## 2.5.5 Supplementary analyses

In addition to completer analysis as the primary, the below estimands will be considered:

1. (Note: Given that the sample size has been largely reduced from 110 to 72, and responder rate to peanut protein is only measured at one single post-dose time point (i.e., at one month), supplementary estimands 1 and 3 that implement multiple imputation will not be performed. Supplementary estimand 1: Participants who do not undergo DBPCFC at one month, due to any reason [including operational complications caused by public health emergency (i.e., COVID-19)] other than AEs will be imputed under Missing at Random (MAR) assumption. The interest lies in the responder status after one month of treatment that would be observed if participants had not discontinued study due to reasons other than AEs before one month of treatment (hypothetical strategy).
2. Supplementary estimand 2: Composite strategy will be considered in addition to hypothetical strategy assuming any participant missing DBPCFC other than due to public health emergency (i.e., COVID-19) or participant missing doses >20% as non-responders.
3. Supplementary estimand 3: Treatment policy will also be considered to show the treatment effect in real-world conditions. Missing DBPCFC outcome in participants who discontinue remibrutinib or who miss more than 20% of study doses throughout the study treatment period or who miss doses  $\geq 3$  consecutive days in the 7 days prior to end-of-treatment visit on Day 26 for reasons other than adverse events before Part 2 DBPCFC visit will be imputed based on copy reference.
4. Supplementary estimand 4: to show treatment effect if treatment failure had not occurred, participants who had dose-limiting symptoms at any dose of the post-treatment blinded OFC to placebo will be considered as non-responders

Intake of rescue medication prior to DBPCFC conducted at end of study after one month of treatment: consider ignorable (treatment policy strategy, reflected in the treatment attribute) for all estimand strategies.

In addition to the primary analysis, we will analyze primary endpoint under primary estimand with Bayesian logistic regression model utilizing historical data on the placebo arm. The priors are the same as the Bayesian logistic regression with weakly informative described in the [Section 2.5.2](#), except for the dose-specific intercept,  $\delta_j$ , that corresponds to the placebo arm (i.e., for  $d_j = 0$ ), which will include information of historical data by using robustified meta-analytic predictive prior (MAP). Placebo information was obtained from both internal and external historic data is presented in [Table 2-2](#). The MAP is derived from historical data using a hierarchical Binomial model as implemented in the RBeST package. The placebo's response probability in the logit scale is the sum of an intercept and trial-specific random effects. For the prior on the intercept, we use a normal distribution with a mean of  $-2.94$  ( $= \text{logit}(0.05)$ ) and a standard deviation of 2. We use the recommended conservative Half-Normal with mean 0 and standard deviation 1 for the prior of the between-trial heterogeneity parameter. The MAP prior on the placebo's response probability in the logit scale, represented numerically using a large MCMC simulation sample, is approximated by a mixture of normal distributions. To further robustify the prior for potential differences across the historical data and the trial data, a non-informative component is added to the mixture prior with a weight of 50% ([Schmidli, et al., 2014](#)). The Bayesian MCP-Mod framework is applied as described in [Section 2.5.2](#). Similar outputs as primary analysis will be generated.

**Table 2-2 Historical trial placebo data from external publications and internal studies**

Table	External data	Number of participants	Responders
Palforzia PII	Yes	26	0
Palforzia PIII	Yes	138	7
CCI			

## 2.6 Analysis supporting secondary objectives

### 2.6.1 Secondary endpoint(s)

The secondary efficacy endpoints will be analyzed as follows:

- Responder status defined as tolerating a single dose of  $\geq 1000$  mg (2044 mg cumulative tolerated dose), and 3000 mg (5044 mg cumulative tolerated dose) peanut protein without dose-limiting symptoms after three weeks placebo plus one week study treatment plus OR after one month of treatment dosing period. The proportion of responders will be analyzed for 1000 mg and 3000 mg peanut protein dose separately utilizing the same logistic regression model proposed for the primary analysis. Proportion of responders and 80% CI will be presented for 1000 mg and 3000 mg peanut protein dose, respectively.
- Categorical summaries will be generated for maximum severity of symptoms occurring at any challenge dose of peanut protein up to and including 3000 mg during the actual DBPCFC conducted after three weeks placebo plus one week study treatment and after one month of treatment dosing period. Symptom severity will be categorized as 4 levels: None, Mild, Moderate, Severe. Proportion of participants will be summarized descriptively by severity levels for the corresponding allergen dose and symptoms.
- (Note: Analysis specified in this bullet point will not be performed because it does not target any objective listed in Protocol) Change in maximum tolerated dose (MTD) of peanut protein without dose-limiting symptoms during the actual DBPCFC after one month of treatment compared to after 1 week of treatment for remibrutinib CCI treatment arms: MTD (log-transformed scale) after one month along with changes from baseline and changes from after 1 week of treatment will be summarized descriptively.

An analysis of covariance (ANCOVA) model for change from baseline in log transformed MTD for actual DBPCFC administered after post-treatment will be fit with terms including, treatment arm, log-transformed baseline total IgE, and log-transformed maximum tolerated allergen dose at baseline. Model adjusted means and 80% CIs will be presented for each of the treatment arms over placebo.

- (Note: Analysis specified in this bullet point will not be performed because it does not target any objective listed in Protocol) Responder status defined as tolerating a maximum single dose of peanut protein without dose-limiting symptoms after 1 week or after one month of treatment.

The proportion of responders for the allergen dose defined as ordinal categorical variable ranging from 0-3000 mg will be analyzed utilizing the proportional odds model. The model will include treatment arm, log-transformed baseline total IgE, and log-transformed

maximum tolerated allergen dose at baseline. Proportion of responders and 80% CI will be presented for each of the peanut allergen dose challenge administered to the participants.

A Kaplan-Meier plot with responder rate vs. peanut allergen dose after one month or after 1 week of treatment will be presented to show any differences across treatment arms (i.e., remibrutinib doses, placebo).

- Change from baseline in peanut-specific IgE and IgG4 after one week/after one month of treatment: Summary statistics, including geometric means and geometric standard deviations, will be presented for peanut-specific IgE and IgG4 along with changes from baseline by time point and treatment group. Change from baseline in log-transformed levels of peanut specific-IgE and peanut specific-IgG4 after one week/one month of treatment will be analyzed using an ANCOVA model with terms for treatment arm, and log-transformed baseline peanut specific-IgE or peanut specific-IgG4.

Ratio of peanut specific IgE to IgG4 for all participants at baseline and post-baseline will be plotted by treatment arm and the descriptive summaries of this ratio will be reported.

- Responder status defined as tolerating a single dose of  $\geq 600$  mg (1044 mg cumulative tolerated dose) of peanut protein without dose-limiting symptoms during the DBPCFC conducted after one week of treatment (3 weeks of placebo + 1 week of remibrutinib treatment vs. placebo). Proportion of responders and 80% CI over placebo will be presented with the same logistic regression model as defined for the primary analysis.
- Change from baseline in wheal size diameters from SPT after one week/after one month of treatment will be analyzed using ANCOVA with baseline wheal size as a covariate and the change from baseline will also be summarized descriptively. Model adjusted means and 80% confidence intervals will be presented for each of the treatment arms over placebo.

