Secondary Objectives	
 
To evaluate the efficacy of oral remibrutinib CCI compared to placebo, as measured by the proportion of participants who can tolerate a single dose of <math>\geq 1000</math> mg (2044 mg cumulative tolerated dose) of peanut protein without dose-limiting symptoms during the DBPCFC after one month of treatment
 
To evaluate the efficacy of oral remibrutinib CCI compared to placebo, as measured by the proportion of participants who can tolerate a single dose of 3000 mg (5044 mg cumulative tolerated dose) of peanut protein without dose-limiting symptoms during the DBPCFC after one month of treatment
 
To evaluate the efficacy of oral remibrutinib CCI compared to placebo, as measured by the maximum symptom severity at any single challenge dose up to and including 1000 mg of peanut protein during the DBPCFC after one month of treatment
 
To evaluate the efficacy of 3 weeks of placebo treatment followed by 1 week of oral remibrutinib CCI treatment compared to one month of placebo treatment, as measured by the proportion of participants who can tolerate a single dose <math>\geq 600</math> mg of peanut protein without dose-limiting symptoms during the DBPCFC after one month of treatment
 
To evaluate the effects of multiple doses of remibrutinib compared to placebo (when applicable), as measured by multiple systemic biomarkers to inform on response to treatment or disease severity
 
To evaluate the safety and tolerability of multiple doses of remibrutinib
 
To assess the ability of remibrutinib to impact skin mast cells through the assessment of allergen-specific skin prick test (SPT)
 
To assess the pharmacokinetics (PK) of remibrutinib
 

Study design	This is a randomized, investigator- and participant-blinded study of remibrutinib compared to placebo, evaluating 5 treatment arms: CCI ██████████ ██████████ for one month OR placebo for 3 weeks, followed by CCI ██████████ for one week OR placebo for one month in 2:2:2:1:1 ratio. Total study treatment duration is one month.

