
 
To evaluate the efficacy of oral remibrutinib CCI compared to placebo, as measured by the proportion of participants who can tolerate a single dose of <math>\geq 1000</math> mg (2044 mg cumulative tolerated dose) of peanut protein without dose-limiting symptoms during the DBPCFC at one month
 
To evaluate the efficacy of oral remibrutinib CCI compared to placebo, as measured by the proportion of participants who can tolerate a single dose of 3000 mg (5044 mg cumulative tolerated dose) of peanut protein without dose-limiting symptoms during the DBPCFC at one month
 
To evaluate the efficacy of oral remibrutinib CCI compared to placebo, as measured by the maximum symptom severity at any single challenge dose up to and including 1000 mg of peanut protein during the DBPCFC at one month
 
To evaluate the efficacy of 3 weeks of placebo treatment followed by 1 week of oral remibrutinib CCI treatment compared to one month of placebo treatment, as measured by the proportion of participants who can tolerate a single dose <math>\geq 600</math> mg of peanut protein without dose-limiting symptoms during the DBPCFC at one month
 
	
 
Responder status defined as tolerating a single dose of <math>\geq 1000</math> mg (2044 mg cumulative tolerated dose) of peanut protein without dose-limiting symptoms during the DBPCFC conducted at one month
 
Responder status defined as tolerating a single dose of 3000 mg (5044 mg cumulative tolerated dose) of peanut protein without dose-limiting symptoms during the DBPCFC conducted at one month
 
Maximum severity of symptoms occurring at any challenge dose of peanut protein up to and including 1000 mg during the DBPCFC conducted at one month. Symptom severity will be categorized as 4 levels: None, Mild, Moderate, Severe
 
Responder status defined as tolerating a single dose of <math>\geq 600</math>mg (1044 mg cumulative tolerated dose) of peanut protein without dose-limiting symptoms during the DBPCFC conducted at one month (3 weeks of placebo + 1 week of remibrutinib treatment vs. one month of placebo)
 

Objective(s)	Endpoint(s)

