## 12.5 Analysis supporting secondary objectives

### 12.5.1 Efficacy and/or Pharmacodynamic endpoint(s)

The secondary efficacy endpoints will be analyzed as follows:

- Responder status defined as tolerating a single dose of  $\geq 1000$  mg (2044 mg cumulative tolerated dose), and 3000 mg (5044 mg cumulative tolerated dose) peanut protein without dose-limiting symptoms after three weeks placebo plus one week study treatment plus OR after one month of treatment dosing period. The proportion of responders will be analyzed for 1000 mg and 3000 mg peanut protein dose separately utilizing the same logistic regression model proposed for the primary analysis. Proportion of responders and 80% Confidence Interval (CI) will be presented for 1000 mg and 3000 mg peanut protein dose, respectively.

Maximum severity of symptoms occurring at any challenge dose of peanut protein up to and including 1000 mg during the DBPCFC conducted after three weeks placebo plus one week study treatment plus OR/ after one month of treatment dosing period. Symptom severity will be categorized as 4 levels: None, Mild, Moderate, Severe. Proportion of participants will be summarized descriptively by severity levels for the corresponding allergic dose and symptoms:

- Change in maximum tolerated dose (MTD) of peanut protein without dose-limiting symptoms during the DBPCFC after one month of treatment compared to after 1 week of treatment for remibrutinib CCI treatment arms: MTD (log-transformed scale) after one month along with changes from baseline and changes from after 1 week of treatment will be summarized descriptively. Responder status defined as tolerating a maximum single dose of peanut protein without dose-limiting symptoms after 1 week or after one month of treatment. The proportion of responders will be analyzed utilizing the proportional odds model. Proportion of responders and 80% CI will be presented for each of the peanut allergen dose challenge administered to the participants. A Kaplan-Meier plot with responder rate vs. peanut allergen dose after one month or after 1 week of treatment will be presented to show any differences across treatment arms (i.e., remibrutinib doses, placebo).

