

To evaluate the efficacy of oral remibrutinib CCI compared to placebo, as measured by the proportion of participants who can tolerate a single dose of <math>\geq 1000</math> mg (2044 mg cumulative tolerated dose) of peanut protein without dose-limiting symptoms during the DBPCFC at one month

To evaluate the efficacy of oral remibrutinib CCI compared to placebo, as measured by the proportion of participants who can tolerate a single dose of 3000 mg (5044 mg cumulative tolerated dose) of peanut protein without dose-limiting symptoms during the DBPCFC at one month

To evaluate the efficacy of oral remibrutinib CCI compared to placebo, as measured by the maximum symptom severity at any single challenge dose up to and including 1000 mg of peanut protein during the DBPCFC at one month

To evaluate the efficacy of 3 weeks of placebo treatment followed by 1 week of oral remibrutinib CCI treatment compared to one month of placebo treatment, as measured by the proportion of participants who can tolerate a single dose <math>\geq 600</math> mg of peanut protein without dose-limiting symptoms during the DBPCFC at one month

To evaluate the effects of multiple doses of remibrutinib compared to placebo (when applicable), as measured by multiple systemic biomarkers to inform on response to treatment or disease severity

	

Responder status defined as tolerating a single dose of <math>\geq 1000</math> mg (2044 mg cumulative tolerated dose) of peanut protein without dose-limiting symptoms during the DBPCFC conducted at one month

Responder status defined as tolerating a single dose of 3000 mg (5044 mg cumulative tolerated dose) of peanut protein without dose-limiting symptoms during the DBPCFC conducted at one month

Maximum severity of symptoms occurring at any challenge dose of peanut protein up to and including 1000 mg during the DBPCFC conducted at one month. Symptom severity will be categorized as 4 levels: None, Mild, Moderate, Severe

Responder status defined as tolerating a single dose of <math>\geq 600</math> mg (1044 mg cumulative tolerated dose) of peanut protein without dose-limiting symptoms during the DBPCFC conducted at one month (3 weeks of placebo + 1 week of remibrutinib treatment vs. one month of placebo)

Change from baseline at Weeks 1 and 4 of:

peanut-specific IgE, including peanut components

peanut-specific IgG4, including peanut components

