## 4 Change to protocol specified analyses

No changes proposed from the protocol specified analyses.

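### SAP 2.6.1 summarises maximum symptom severity up to 3000 mg, while the protocol and the SAP's own Table 1-1 define this secondary endpoint up to 1000 mg and SAP Section 4 declares no change

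*SAP*

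**What the plan says.** The ceiling is 1000 mg in every protocol statement of this endpoint:

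- Protocol summary, secondary objective: "maximum symptom severity at any single challenge dose up to and including 1000 mg of peanut protein".
- Protocol Table 2-1, objective: "maximum symptom severity at any single challenge dose up to and including 1000 mg of peanut protein during the DBPCFC at one month". The endpoint beside it has the same limit: "up to and including 1000 mg during the DBPCFC conducted at one month".
- Protocol 12.5.1, analysis text: "Maximum severity of symptoms occurring at any challenge dose of peanut protein up to and including 1000 mg during the DBPCFC conducted after three weeks".

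SAP Table 1-1 repeats 1000 mg in both columns; its endpoint reads "Maximum severity of symptoms occurring at any challenge dose of peanut protein up to and including 1000 mg during the DBPCFC conducted at one month".

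SAP 2.6.1, which governs what is produced, instead covers "maximum severity of symptoms occurring at any challenge dose of peanut protein up to and including 3000 mg during the actual DBPCFC". The SAP document history for 14 May 2025 explains this by calling the protocol's 1000 mg a typographical error. SAP Section 4 states: "No changes proposed from the protocol specified analyses".

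Protocol and SAP agree that the analysis is descriptive: proportions in four severity levels, shown by allergen dose and symptom, with no hypothesis test.

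**The concern.** The conflict lies between passages of current text. SAP 2.6.1 disagrees with SAP Table 1-1, with SAP Section 4 and with the protocol, so it is more than a change log describing superseded wording.

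Two things are at stake. First, a stated secondary objective loses the summary planned for it, and a reader who relies on Section 4 would not know. Second, the two ceilings measure different things. The last challenge step goes only to participants who have already shown protection through 1000 mg, and far more of these are expected on remibrutinib than on placebo. Reactions at that step would be counted in the maximum as if they belonged to the 1000 mg question.

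The SAP also applies its own standard unevenly. The same section drops two other analyses because they serve no objective listed in the protocol, yet a 3000 mg ceiling matches no listed severity objective either.

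**Working it through.** **Dose steps.** Protocol 16.4.3 can be reproduced: 1 + 3 + 10 + 30 + 100 + 300 + 600 + 1000 = 2044 mg cumulative, and adding 3000 gives 5044 mg. Both match the plan. The only step above 1000 mg is 3000 mg.

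**Direction for an individual.** Protocol 16.4.6 forbids the next dose once a dose-limiting symptom occurs. Someone who reacts at or below 1000 mg never takes 3000 mg, and their maximum is the same under either ceiling. For someone who passes 1000 mg, the maximum over nine doses cannot be below the maximum over eight. In 100,000 simulated challenge paths under this rule, the 3000 mg maximum was never lower and differed only in paths that reached 3000 mg.

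**Direction for the contrast.** Let q be the share passing 1000 mg and taking 3000 mg, and h the share of those who react at 3000 mg, with subscripts A (active) and P (placebo). Treat dose-limiting as moderate or severe, and define the contrast as the placebo share minus the active share with moderate or severe symptoms.

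- 1000 mg ceiling: (1 − qP) − (1 − qA) = qA − qP
- 3000 mg ceiling: qA(1 − hA) − qP(1 − hP)
- Change: qP·hP − qA·hA

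The contrast falls only if qA·hA exceeds qP·hP.

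**Inputs.** None of the four rates is in the documents.

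- qP = 0.043 is a proxy from the visible rows of SAP Table 2-2: (0 + 7)/(26 + 138) = 7/164 = 4.3%. Other rows are redacted.
- qA = 0.60 is an assumption. It lies below the 80% remibrutinib response rate in the Amendment 02 rationale, which is an upper bound if it refers to the 600 mg primary endpoint.
- hP = 1 is an assumption; hA is varied.

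**Results.** With the 1000 mg ceiling the contrast is 0.60 − 0.043 = 55.7 points.

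| hA | 3000 mg ceiling: 0.60 × (1 − hA) | Change (points) |
|---|---|---|
| 0.50 | 30.0 | −25.7 |
| 0.25 | 45.0 | −10.7 |
| 0.10 | 54.0 | −1.7 |
| 0 | 60.0 | +4.3 |

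Break-even is hA = qP/qA = 0.043/0.60 = 7.2%.

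**Range.**

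- With qP = 0.043, break-even is 5.4% at qA = 0.8 and 10.7% at qA = 0.4.
- With qP = 0.15 and qA = 0.60, the 1000 mg contrast is 45.0 points and break-even rises to 25%. The 3000 mg contrast is then 30.0, 45.0, 54.0 or 60.0 for hA = 0.50, 0.25, 0.10 or 0.
- With the 7 planned placebo completers, the chance that none reaches 3000 mg is 0.957^7 = 0.735 at qP = 0.043 and 0.85^7 = 0.321 at qP = 0.15. In that event the observed contrast can only fall or stay the same.

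**The case against.** **Consequence.** The endpoint is descriptive, carries no alpha and has no part in the MCP-Mod analysis or the power statement. If the contrast shrinks, that works against remibrutinib. The change is disclosed with a reason in the document history, before final database lock. All of this stands and limits the weight of the point.

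**The 1000 mg result may be recoverable.** The planned display is by allergen dose, and the 1000 mg and 3000 mg responder endpoints keep their own logistic regressions. This stands in part. Moderate or severe symptoms end the challenge, so those counts could probably be added over the steps up to 1000 mg. The split between None and Mild could not, because one participant can be mild at several doses. By-dose proportions are not each participant's maximum.

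**Stronger readings that the documents do not support.**

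- A reader might infer that the higher ceiling necessarily dilutes the treatment effect. It does not: if remibrutinib also protects at 3000 mg, the contrast is unchanged or somewhat larger.
- A reader might infer that the typo explanation is disproved. Consistent use of 1000 mg in objective, endpoint and analysis text makes it weakly supported, but an error can be copied forward and intent cannot be settled.
- A reader might object that the 3000 mg version nearly repeats the 3000 mg responder endpoint. A 1000 mg ceiling nearly repeats the 1000 mg responder endpoint in the same way, so this favours neither.
- A reader might suspect that the change followed sight of unblinded data. The milestone beside the SAP date is redacted, and nothing supports that inference.

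**Conclusion.** The conflict is real. The secondary endpoint defined in the protocol and in SAP Table 1-1 has no matching summary in SAP 2.6.1, and the no-change statement in Section 4 is inaccurate.

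That the higher ceiling can only raise recorded severity, and only in participants who passed 1000 mg, follows from the stopping rule and needs no assumption. A smaller contrast is the expected direction when many more remibrutinib than placebo participants reach 3000 mg and some of them react, but it is conditional. In the main illustration the change runs from −25.7 to +4.3 points.

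Those figures rest on assumed rates and on equating dose-limiting with moderate or severe. The equation is approximate: protocol 16.4.6 also makes a challenge positive for a combination of mild symptoms at the investigator's discretion, or for any symptom needing rescue medication.

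No test, type I error rate or primary conclusion is affected. The defect is one of fidelity to the protocol and accurate reporting of a named secondary endpoint.

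**What to change.** - In SAP 2.6.1, report maximum severity with the 1000 mg ceiling as the protocol-defined secondary endpoint.
- Keep the 3000 mg version as an additional descriptive table, labelled as such.
- Make SAP 2.6.1 and SAP Table 1-1 agree.
- Remove the statement that 1000 mg is a protocol typo. If 3000 mg was always intended, the protocol objective and endpoint need amending, because the current protocol text still says 1000 mg.
- Replace the no-change statement in SAP Section 4 with a list of remaining departures. These include the supplementary estimands that SAP 2.5.5 says will not be run and the two secondary analyses that SAP 2.6.1 drops.

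The cost is SAP wording and one extra descriptive table from data already collected.

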## 2.2 Secondary estimands

Not Applicable.

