## **12 Data analysis and statistical methods**

Any data analysis carried out independently by the investigator should be submitted to Novartis before publication or presentation.

Statistical summaries will be generated by treatment arm and overall for disposition, demographics and any baseline characteristics. Unless specified otherwise, all endpoints relevant to efficacy, safety, PK, PD and biomarkers will be summarized by treatment arm (i.e., LOU064 or placebo).

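### The secondary objective on maximum symptom severity is a comparison with placebo, but the plan prespecifies only descriptive percentages, with no effect estimate or interval

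*SAP*

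**What the plan says.** The objective in Protocol Table 2-1, repeated in SAP Table 1-1, is to evaluate the efficacy of remibrutinib "compared to placebo, as measured by the maximum symptom severity at any single challenge dose up to and including 1000 mg of peanut protein". The scale is fixed in the endpoint column: "Symptom severity will be categorized as 4 levels: None, Mild, Moderate, Severe".

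Protocol 12.5.1 gives the analysis: "Proportion of participants will be summarized descriptively by severity levels for the corresponding allergic dose and symptoms". SAP 2.6.1 keeps the descriptive approach but changes the dose range: "Categorical summaries will be generated for maximum severity of symptoms occurring at any challenge dose of peanut protein up to and including 3000 mg". It then adds: "Proportion of participants will be summarized descriptively by severity levels for the corresponding allergen dose and symptoms". The by-arm layout comes from Protocol section 12, under which "all endpoints relevant to efficacy, safety, PK, PD and biomarkers will be summarized by treatment arm".

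Protocol 2.2 lists secondary estimands as "Not Applicable", so no summary measure for this endpoint is defined there either.

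**The concern.** An objective worded as a comparison needs a stated measure of the difference and of its uncertainty. Here the reader will get percentages in four ordered categories per arm, further divided by challenge dose and symptom, and nothing that combines them into an effect. The ordering of the categories is not used. Whoever writes the report must then choose, after seeing the data, which cells or cut-points to compare.

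The split by dose adds a second difficulty. The challenge stops at the first dose-limiting symptom (Protocol 16.4.6), so participants at the high doses are those who tolerated all lower ones. The plan states no denominator for these cells.

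**Working it through.** **1. Is the comparison supplied anywhere else?** SAP 2.6.1 treats the secondary efficacy endpoints as follows.

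| Endpoint | Planned analysis |
|---|---|
| Responder at 1000 mg and at 3000 mg | Primary logistic model, proportion with 80% CI |
| Responder at 600 mg, 1-week arm | Primary logistic model, 80% CI over placebo |
| Peanut-specific IgE and IgG4 | ANCOVA |
| Skin prick wheal | ANCOVA, 80% CI over placebo |
| Maximum symptom severity | Descriptive percentages only |

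The SAP does contain a proportional-odds model (2.6.1 and 5.5). Its outcome is the tolerated allergen dose, and 2.6.1 marks it as not to be run because it serves no protocol objective. Severity does serve an objective and has no model.

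**2. Expected numbers.** Inputs are 72 participants, allocation 2:2:2:1:1 and about 10% discontinuation (Protocol 12.8).
- One-month arm: 72 × 2/8 × 0.9 = 16.2.
- Placebo: 72 × 1/8 × 0.9 = 8.1.

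These match the upper end of the stated 14 to 16 and 7 to 8. The lower end means 22% loss (1 − 14/18 = 1 − 7/9 = 0.22).

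**3. Precision that an ordinal contrast would have.** The documents give no severity distribution, so three placebo distributions were assumed (None/Mild/Moderate/Severe): 2/8/60/30%, 5/15/55/25% and 5/25/50/20%. Whitehead's variance for a common odds ratio uses V = n0·n1·N / [3(N+1)²] × (1 − Σp̄³), where p̄ are the pooled category proportions. Then SE = 1/√V, and the 80% CI is OR ×/÷ exp(1.2816 × SE).

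Worked case: middle distribution, true OR 5, 7 versus 14 completers.
- Remibrutinib distribution about 21/35/38/6%; pooled about 15.7/28.3/43.7/12.3%; Σp̄³ about 0.112.
- V = 7·14·21/(3·22²) × 0.888 = 1.417 × 0.888 = 1.26, so SE = 0.89.
- Factor = exp(1.2816 × 0.89) ≈ 3.13; interval 1.6 to 15.7.

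| True OR (middle distribution) | 80% CI, 7 vs 14 | 80% CI, 8 vs 16 |
|---|---|---|
| 3 | 0.94 to 9.6 | 1.02 to 8.8 |
| 5 | 1.6 to 15.7 | 1.7 to 14.5 |
| 10 | 3.2 to 30.8 | 3.5 to 28.5 |

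Over all three distributions and both sample sizes, SE runs from 0.82 to 0.97 and the factor from about 2.9 to 3.5.

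**4. Would the model fit?** In 300 simulated trials per scenario (7 versus 14, middle distribution, no covariates), an unpenalised proportional-odds fit gave a usable estimate in 94%, 91% and 86% of trials at OR 3, 5 and 10. A rule for separation is therefore needed. The weakly informative priors in SAP 2.5.2 cover arm intercepts and covariates of a binary model, not ordinal cutpoints.

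**5. How many placebo participants reach the 1000 mg challenge dose?** Only those who tolerate 600 mg. The two visible rows of SAP Table 2-2 show 0/26 and 7/138 placebo responders, that is 7/164 = 4.3%, taking responder there in the primary-endpoint sense. SAP 2.5.5 centres the prior for the placebo rate at 5%. With 7 placebo completers, 0.043 × 7 = 0.30 and 0.05 × 7 = 0.35 participants are expected. At an assumed 10% it is 0.7. Other rows of the table are redacted.

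**The case against.** The best defence is that the choice was deliberate. Both documents state it, the only formal hypothesis test is MCP-Mod on the primary endpoint, and tabulating a non-confirmatory phase 2 endpoint with 7 to 8 placebo completers is defensible. That stands as a reason to rate the issue low. It does not explain why endpoints at the same sample size are modelled, and small numbers are a reason to show the uncertainty.

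Several stronger readings are tempting but not supported.
- *That the trial could never state an effect.* Counts by arm would let anyone compute a difference and an exact interval. What is missing is prespecification.
- *That an ordinal analysis is needed for power.* Under assumed splits, with 14 versus 7 and one-sided 10%, a rank comparison and a moderate-or-severe comparison performed alike: 98% and 97%, 89% and 89%, 61% and 67%. The gain is one prespecified summary using the whole scale.
- *That severity merely subdivides the responder result.* Protocol 16.4.6 also counts as dose-limiting a combination of mild symptoms, at the investigator's discretion, and any symptom needing rescue medication. A participant graded Mild can be a non-responder.
- *That almost no placebo participant reaches 600 mg.* That depends on tolerance of 300 mg, which the documents do not give. The calculation supports only the 1000 mg cell.
- *That every other challenge endpoint explicitly gets an interval against placebo.* For 1000 and 3000 mg this follows from reuse of the primary model. Only the 1-week endpoint says so outright.

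**Conclusion.** The mismatch holds: a comparative secondary objective has a purely descriptive analysis, with no prespecified effect measure or interval in either document. This rests on the text and needs no assumption. The size is modest. The endpoint is not confirmatory, and any interval will be wide, with the odds ratio multiplied or divided by about 3 under the assumed severity distributions. By-dose percentages at 1000 mg cannot carry the comparison, because fewer than one placebo participant is expected there if 600 mg tolerance is 10% or lower.

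One inconsistency must be settled first. SAP Table 1-1 stops at 1000 mg, whereas SAP 2.6.1 runs to 3000 mg. The SAP document history calls the 1000 mg figure a protocol typo, yet SAP section 4 says nothing departs from the protocol analyses. The two ceilings give different outcomes: a participant symptom-free through 1000 mg who reacts severely at 3000 mg is None under one and Severe under the other.

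**What to change.** In the SAP:
1. Reconcile the dose ceiling between Table 1-1, 2.6.1 and section 4, and with Protocol Table 2-1, and record the decision.
2. Keep the frequency table by arm. Add one analysis of each participant's maximum severity. For each remibrutinib arm versus placebo, report the Mann-Whitney probability of lower severity (ties counted half) with an 80% CI and a named interval method. A proportional-odds common odds ratio with the primary-model covariates (log baseline total IgE, baseline tolerated dose) and 80% CI is an alternative.
3. If the proportional-odds model is chosen, state what is done under separation, with priors that also cover the cutpoints.
4. In any by-dose table, use all challenged participants in the arm as the denominator and show *challenge already stopped* as a category.

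If the sponsor wants description only, the objective should be reworded so that it no longer promises a comparison.

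The cost is SAP wording and one output on data already collected. The drawbacks are wide intervals and a proportional-odds assumption that cannot be checked well with 7 to 8 placebo completers. The rank-based probability avoids that assumption but is not covariate-adjusted.
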